##### b. Exclusion criteria

1. History of hypersensitivity to previous influenza vaccination or severe hypersensitivity to eggs/egg protein;
2. History of Guillain-Barre syndrome;
3. Evidence of hematologic malignancy or disease relapse post-transplant (stable mixed chimerism is permitted);
4. History of receiving current seasonal influenza vaccine post-transplant;
5. Pregnant female;
6. History of proven influenza disease after September 1, 2018 prior to enrollment;
7. Non-allogeneic (e.g. autologous) or syngeneic hematopoietic SCT recipients;
8. History of known active infection with HIV
9. History of cirrhosis
10. History of known latex hypersensitivity;
11. Subjects who have received stem cell boost or delayed donor lymphocyte infusion within 90 days of enrollment, including day of enrollment
12. Receipt of. IVIG/SCIG  $< 28$  days prior to vaccination

**Criteria for temporarily delaying vaccine administration:** The following conditions are temporary or self-limiting, and a subject may be included in the study once the condition has resolved, provided that the subject is otherwise eligible:

1. Fever  $\geq 100.4^{\circ}\text{F}/38.0^{\circ}\text{C}$  (oral measurement), or an acute illness within 48 hours of enrollment
2. Receipt of any live vaccines within four weeks or any inactivated vaccines within two weeks prior to potential study vaccination.

Note: if patients were eligible for vaccine 1, they will be eligible to receive vaccine 2 regardless of any changes on their GVHD status, unless it is deemed not medically safe to receive influenza vaccine.

**For subjects who were enrolled and vaccinated in 2017-18, and 2018-19, the goal is to enroll these same subjects who participated the previous influenza season year and then administer the same vaccination as the previous year. These subjects are referred to as repeaters.**

**For example, subjects enrolled in 2017-18 year were eligible to enroll again in 2018-19 as repeaters. For subjects enrolled in 2018-19 year and received at least one vaccine, will be eligible to be enrolled as repeaters for 2019-2020 season.**

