**2. Exclusion Criteria for Repeaters**

- a. Evidence of hematologic malignancy or disease relapse post-transplant (stable mixed chimerism is permitted);
- b. History of receiving current seasonal influenza vaccine post-transplant.
- c. Pregnant female.
- d. History of proven influenza disease after September 1, 2019 prior to enrollment.
- e. History of known active infection with HIV
- f. History of cirrhosis
- g. Subjects who have received stem cell boost or delayed donor lymphocyte infusion within 90 days of enrollment, including day of enrollment
- h. Receipt of IVIG/SCIG  $< 28$  days prior to calendar day of vaccination

**Criteria for temporarily delaying vaccine administration:** The following conditions are temporary or self-limiting, and a subject may be included in the study once the condition has resolved, provided that the subject is otherwise eligible: 1. Fever  $\geq 100.4^{\circ}\text{F}/38.0^{\circ}\text{C}$  (oral measurement), or an acute illness within 48 hours of enrollment 2. Receipt of any live vaccines within four weeks or any inactivated vaccines within two weeks prior to study vaccination.

Note: if patients were eligible for vaccine 1, they will be eligible to receive vaccine 2 regardless of any changes on their GVHD status, unless it is deemed not medically safe to receive influenza vaccine.

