### 13. Study Visit Schedule: (see Table 3 for details)

- a. **Screening:** Subjects will be screened by history and physical exam to make sure that all eligibility criteria are met. No baseline laboratory screening will be performed prior to enrollment. However, if CBC d/p, quantitative CD4, CD8, CD19, and IgG/IgM are obtained as part of standard of care prior to enrollment and on the same calendar day as vaccination, these data will be collected and will not need to be repeated after consent is signed. In addition, prior to visit 1, consent may be obtained.
- b. **Enrollment/Baseline:** Prior to each vaccination, inclusion and exclusion criteria, as well as any reason to delay vaccination will be reviewed.
- c. **Follow up:** Follow-up telephone and/or electronic communication will be completed both 1-3 and 8-10 days after each vaccination visit. If the subject is seen as part of the optional visit and this visit is within the 8-10 days communication window period, this would replace the 8-10 day telephone and/or electronic communication.
- d. **Final Study Visit:** The final visit will be  $180 \pm 56$  after visit 3.
- e. **Unscheduled Visits:**

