### 14. Study Procedures/Evaluation:

#### **Screening Periods/Supplemental Visit, prior to Visit 1, Day 0.**

- Subjects are able to sign written informed consent prior to Visit 1. Also, if individuals sign a consent and are later deemed not eligible for vaccination on that day, this will be listed as a supplemental visit with screen failure. If the subject was temporarily unable to receive vaccine and later becomes eligible (as in the case of recent prior other vaccine receipt) they can proceed with the following study procedures.

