#### **Visit 1: Day 0:**

- Subject will sign written Informed Consent if not already signed prior to Visit 1.
- Brief review of Medical history
  - Inclusion/exclusion criteria will be checked.
  - Prior/concomitant medications will be recorded.
  - Written documentation of prior influenza immunizations post-transplant will be collected.
- Targeted physical examination will be conducted including measurement of oral temperature (must be  $\leq 100.4^{\circ}\text{F}/38^{\circ}\text{C}$ ). Except for oral temperature, if a physical exam is completed as a part of standard of care, another physical exam does not need to be completed.
- For females of childbearing potential a pregnancy test will be performed.

- Approximately 30-60 mL of blood will be collected by venipuncture or from a central line prior to vaccination for HAI and MN assays to influenza virus antigens, phenotypic B, and T cell responses, B and T cell specific influenza responses, CBC d/p, quantitative CD4+/CD8+/CD19+ levels, and quantitative serum IgG and IgM concentrations (if CBC d/p, quantitative CD4+, CD8+, CD19+, IgM, and IgG are obtained as part of standard of care prior to enrollment and on the same calendar day as vaccination, these data will be collected and will not need to be repeated).
- Study vaccine will be administered.
- Study staff will observe the subjects closely for at least 15 minutes post-vaccination, with appropriate medical treatment readily available in case of rare anaphylactic reaction following the administration of vaccines.
- If IVIG/SCIG is given the same day, it must be given after the vaccination, and a second blood draw will be obtained post-IVIG/SCIG if administered on same calendar day.
- A memory aid form with reaction measurements, a measurement gauge, thermometer and instructions will be provided for the subject to record oral temperatures and any general or local reactions occurring during the vaccination day (day 0) and the next 7 days. Information on the memory aid form will be collected from the subject through telephone calls and/or electronic communication in the week following vaccination or received by mail. . If memory aid data were not received by any of the methods mentioned, subjects may return it on the day of their next visit.

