**Visit 2: Days 28-42:**

- Solicited AEs/unsolicited AEs will be reviewed and recorded.
- Medical history changes

- Concomitant medications will be recorded.
- Inclusion/exclusion criteria will be checked- patients will be eligible to receive vaccine 2 if they received vaccine 1, regardless of GVHD status changes but the changes need to be documented.
- Targeted physical examination will be conducted including measurement of oral temperature (must be <100.4°F/38°C). If a physical exam is completed as a part of standard of care, another physical exam does not need to be completed.
- For females of childbearing potential a pregnancy test will be performed
- Approximately 30-60 mL of blood will be collected by venipuncture or from a central line prior to vaccination for HAI and MN assays to influenza virus antigens, phenotypic B, and T cell responses, B and T cell specific influenza responses, CBC d/p, quantitative CD4+/CD8+/CD19+ levels, and quantitative serum IgG and IgM concentrations.
- Study vaccine will be administered
- Study staff will observe the subjects closely for at least 15 minutes post-vaccination, with appropriate medical treatment readily available in case of rare anaphylactic reaction following the administration of vaccines.
- If IVIG/SCIG is given the same day, it must be given after the vaccination, and a second blood draw will be obtained post-IVIG/SCIG if administered on same calendar day.
- A memory aid form with reaction measurements, a measurement gauge, thermometer and instructions will be provided for the subject to record oral temperatures and any general or local reactions occurring during the vaccination day (day 0) and the next 7 days. Information from the memory aid form will be collected from the subject through telephone calls or emails in the week following vaccination. If memory aid data were not received by any of the methods mentioned, subjects may return it on the day of their next visit.
- The subject will be given contact information for study personnel. The subject will be educated about any potential reactions following vaccination. They will be instructed to contact study personnel for reactions that are Grade 3, as well as any other medical event that is concerning to subject.
- A nasal swab for PCR testing for influenza and other respiratory viruses will be obtained regardless of symptoms.

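### The fever rule for delaying vaccination and the Visit 1 temperature limit disagree at exactly 38.0°C/100.4°F, and the acute-illness rule is timed to enrolment, so its use before dose 2 is unclear

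*Combined protocol and SAP*

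**What the plan says.** **Delay criteria (section C.4, new subjects and repeaters).** Item 1 of each list delays vaccination for an oral temperature at or above 100.4°F/38.0°C, or for recent acute illness. For new subjects the text reads "oral measurement), or an acute illness within 48 hours of enrollment", and the repeaters' list repeats "or an acute illness within 48 hours of enrollment". Item 2 concerns receipt of other vaccines and is timed to dosing. For new subjects it reads "any inactivated vaccines within two weeks prior to potential study vaccination".

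**Visit procedures (section C.14).** At Visit 1, "Targeted physical examination will be conducted including measurement of oral temperature", with a stated limit of at or below 100.4°F/38°C. At Visit 2 the limit is strict: "oral temperature (must be <100.4°F/38°C".

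**Grading (Table 5).** Grade 1 fever begins at 38.0°C (100.4°F).

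**Review before dosing (section C.13.b).** "Prior to each vaccination, inclusion and exclusion criteria, as well as any reason to delay vaccination will be reviewed". Table 3 places the eligibility check and the oral temperature at both Visit 1 and Visit 2.

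**Consent (section C.14, screening).** "Subjects are able to sign written informed consent prior to Visit 1". The protocol does not define the moment of enrolment relative to consent or dosing.

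**The concern.** A rule that decides whether a subject is dosed on a given day should give the same answer wherever it is stated. Here it does not, in two respects.

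First, the sign of the temperature inequality changes between the delay list, Visit 1 and Visit 2. The Visit 1 sign lets through a reading that the protocol itself grades as fever.

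Second, the illness criterion is fixed to an event that happens once, while subjects are vaccinated twice, 28-42 days apart. For a subject without fever who is acutely ill before dose 2, a 48-hour window around enrolment has no obvious meaning.

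What is at stake is the safety comparison. Section 17.c takes as its main safety measure the proportion of subjects with at least one solicited adverse event, and states no relatedness filter. Symptoms of an illness already present at dosing could be recorded on the Day 0-7 memory aid as fever, malaise, headache or myalgia. With four sites, the same patient could also be handled differently by site or by visit.

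**Working it through.** **Step 1: units.** 38.0 × 1.8 + 32 = 100.4. The Celsius and Fahrenheit cut-offs agree, so the conflict lies only in the inequality sign.

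**Step 2: temperature rules side by side.**

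| Oral temperature | Delay list (C.4, both versions) | Visit 1 check (C.14) | Visit 2 check (C.14) | Table 5 |
|---|---|---|---|---|
| Below 38.0°C | no delay | passes | passes | no fever |
| Exactly 38.0°C | delay | passes | fails | Grade 1 |
| Above 38.0°C | delay | fails | fails | Grade 1 or higher |

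The rows differ only at 38.0°C, and only the Visit 1 entry is out of line there. Visit 2 agrees with the delay list.

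**Step 3: reference times side by side.**

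| Rule | Timed to |
|---|---|
| Delay item 1, acute illness (new subjects and repeaters) | enrolment |
| Delay item 2, other vaccines (new subjects and repeaters) | study vaccination |
| Exclusion 11 (cell boost or donor lymphocytes; item g for repeaters) | enrolment |
| Exclusion 12 (immunoglobulin; item h for repeaters) | vaccination |
| Review of delay reasons, section C.13.b | each vaccination |

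The protocol uses the two reference times for different rules, so enrolment in item 1 cannot simply be assumed to mean vaccination. Section C.13.b requires the review to happen before dose 2. The criterion being reviewed still carries an enrolment window.

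**Step 4: possible size.** The documents give no rate of illness at dosing, so this is an illustration on assumed inputs. Let p be the true proportion with a systemic event, and q the proportion who are acutely ill at dose 2, are not deferred and all report an event, with q equal in both arms.

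- Observed rate = p + (1 − p) × q
- Observed difference = (1 − q) × (true difference)

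With assumed p of 40% (high dose) and 30% (standard dose), and q = 5%:

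- High dose: 0.40 + 0.60 × 0.05 = 0.430
- Standard dose: 0.30 + 0.70 × 0.05 = 0.335
- Difference: 0.430 − 0.335 = 0.095, against 0.100 without the illness

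As q runs from 0 to 5%, the difference runs from 10.0 to 9.5 points. The relative shrinkage equals q whatever the two underlying rates are.

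**The case against.** The best defence is that the sections are meant to be applied together. A limit that a temperature must not exceed is a ceiling, not an instruction to vaccinate. Visit 1 also requires the eligibility criteria to be checked, and section C.13.b adds the reasons for delay, so a careful site would still delay at 38.0°C. Section C.13.b sits under a label that includes enrolment, which suggests that the authors meant the check before every dose. The same section speaks of tests done before enrolment on the calendar day of vaccination, which places enrolment at Visit 1 and not at an earlier consent. Section C.8 covers intercurrent illness, and the note after the delay criteria keeps a medical-safety exception for dose 2. A respiratory virus swab is taken at both dosing visits, which helps to identify illness that was already present.

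Much of this stands, and it rules out three stronger readings that a reader might infer:

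- **That febrile subjects in general may be dosed at Visit 1.** Any reading above 38.0°C is barred in every place, and temperature is checked at both dosing visits.
- **That an acute illness before dose 2 does not defer it.** Section C.13.b requires delay reasons to be reviewed before each vaccination, so this does not follow. The text leaves the application unclear; it does not rule deferral out.
- **That every second dose is affected.** Only an afebrile, acutely ill subject whom staff do not defer is affected.

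The defence does not remove the mismatch at 38.0°C, because a site working from the Visit 1 procedures sees a different limit from the one in the list. Nor does it supply a window for illness before dose 2. The medical-safety exception is discretionary and is written around changes in GVHD. The Visit 2 text leans towards giving dose 2 to anyone who received dose 1.

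**Conclusion.** The plan is wrong as written, but the point is minor. The temperature rules contradict each other at one value, 38.0°C/100.4°F, and only at Visit 1. A subject at that reading could pass the Visit 1 temperature check while already meeting the Table 5 definition of Grade 1 fever. The illness criterion has a reference time that does not carry over clearly to dose 2.

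The expected effect on the safety comparison is very small. The half-point change in the working rests on assumed event rates, an assumed 5% illness rate at dose 2, no deferral at all, and an event reported by every ill subject. These assumptions are pessimistic. Sample size and the immunogenicity analysis figures are unaffected.

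The scope for change is also limited. Section C.4 gives 2017-18 and 2018-19 as the enrolment years for new subjects and describes their criteria as already used. This version is dated August 12, 2019. A correction can therefore act prospectively only for the 2019-20 repeaters.

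**What to change.** Reconcile both sets of delay criteria in section C.4, the pre-vaccination review in section C.13.b, and the Visit 1 and Visit 2 procedures in section C.14. They should state one temperature inequality, and one explicit reference time for acute illness that works for both doses. Which inequality and which window to use is a clinical decision for the sponsor; this review does not propose either.

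Apply the reconciled wording prospectively to the 2019-20 repeaters. For the completed seasons, leave the criteria as the record of what was used. Add a short note on which rule each site applied at 38.0°C and for illness before dose 2.

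The cost is wording in a few places and the documentation note, with at most a short deferral for an occasional subject, depending on the rule chosen. No analysis needs to change.

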**Enrollment Criteria for Repeaters - Subjects who Participated in a previous influenza season:**

- Repeaters will retain their original study ID, their randomization number and receive the same blinded vaccine.
- Previous screen failures will not be enrolled.
- If visit 4 from previous influenza season year and visit 1 from current influenza season year occur on the same day, lab results from visit 4 that same day prior to consent can be part of visit 1.

**1. Inclusion Criteria for Repeaters**

- a. Available for duration of study;
- b. Can be reached by telephone and/or electronic communication
- c. Patients with stable GVHD for at least 4 weeks will be eligible (stable is defined as no major change in systemic immunosuppressive therapy for worsening GVHD; adjustment of actual dose to obtain a stable target level is acceptable).
- d. Subjects must have a platelet count of  $\geq 30,000$  to receive the immunizations. Patients requiring platelet transfusions are eligible to enroll and must have a platelet count  $\geq 30,000$  within 72 hours prior to their immunization, or platelet count  $\geq 75,000$  without transfusion documented within 30 days for subjects  $< 12$  months post-transplant and within 90 days for subjects 12-23 months post-transplant.

**2. Exclusion Criteria for Repeaters**

- a. Evidence of hematologic malignancy or disease relapse post-transplant (stable mixed chimerism is permitted);
- b. History of receiving current seasonal influenza vaccine post-transplant.
- c. Pregnant female.
- d. History of proven influenza disease after September 1, 2019 prior to enrollment.
- e. History of known active infection with HIV
- f. History of cirrhosis
- g. Subjects who have received stem cell boost or delayed donor lymphocyte infusion within 90 days of enrollment, including day of enrollment
- h. Receipt of IVIG/SCIG  $< 28$  days prior to calendar day of vaccination

**Criteria for temporarily delaying vaccine administration:** The following conditions are temporary or self-limiting, and a subject may be included in the study once the condition has resolved, provided that the subject is otherwise eligible: 1. Fever  $\geq 100.4^{\circ}\text{F}/38.0^{\circ}\text{C}$  (oral measurement), or an acute illness within 48 hours of enrollment 2. Receipt of any live vaccines within four weeks or any inactivated vaccines within two weeks prior to study vaccination.

Note: if patients were eligible for vaccine 1, they will be eligible to receive vaccine 2 regardless of any changes on their GVHD status, unless it is deemed not medically safe to receive influenza vaccine.

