#### 4. Study Population:

1. **A target of at least 138 new subjects who received an allogeneic HSCT over two enrollment years: 2017-18 and 2018-2019. The following were the inclusion/exclusion criteria that were used:**

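### The repeater exclusion list does not expressly exclude Guillain-Barre syndrome or known latex hypersensitivity, although both bar new subjects

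*Combined protocol and SAP*

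**What the plan says.** Section C.4 (Study Population) introduces its first set of criteria with "A target of at least 138 new subjects who received an allogeneic HSCT over two enrollment years: 2017-18 and 2018-2019". The exclusions that follow in C.4.b number twelve. Item 1 is "History of hypersensitivity to previous influenza vaccination or severe hypersensitivity to eggs/egg protein", item 2 is "History of Guillain-Barre syndrome", and item 10 is known latex hypersensitivity.

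Returning subjects have separate criteria. They keep their randomization number and receive the same blinded vaccine, and earlier screen failures cannot return. Their exclusions stand under the heading "Exclusion Criteria for Repeaters" as items a to h. Item d is dated for the coming season: "History of proven influenza disease after September 1, 2019 prior to enrollment". Items e and f are "History of known active infection with HIV" and "History of cirrhosis". None of the eight items concerns Guillain-Barre syndrome, latex, or vaccine or egg allergy, and the list does not refer back to C.4.b.

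Two later sections touch the same conditions. C.11.b says that people with egg allergy or an allergic reaction to an earlier influenza vaccine are not enrolled. It also warns that the syringe tip caps may contain latex, but the exclusion that closes the paragraph names only vaccine and egg hypersensitivity. C.11 and C.12.a mention Guillain-Barre syndrome only as an event that has been reported after vaccination.

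**The concern.** The protocol treats Guillain-Barre syndrome and latex hypersensitivity as reasons to withhold these vaccines from a new subject. A repeater would receive up to two more doses of the same products, and the documents give no reason for a different rule. Passing C.4.b a season earlier does not settle the matter, because either condition can develop or first be recognised in between.

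The gap lies in the rule and not in detection. The Visit 1 history and examination, and the instruction to subjects to report medical events that worry them (C.14), may well bring the condition to light. When they do, no listed repeater criterion says that the person is excluded, and sites could decide differently. What is at stake is consistent protection of participants. Repeaters serve secondary objective viii, so the primary comparison is not involved.

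**Working it through.** The protocol states no figure on this point, so the check is a comparison of lists followed by a search for other text that would fill the gap.

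**Step 1: match the two lists.**

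| C.4.b item | Subject | Repeater item |
|---|---|---|
| 1 | Vaccine or egg hypersensitivity | none |
| 2 | Guillain-Barre syndrome | none |
| 3 | Malignancy or relapse | a |
| 4 | Current seasonal vaccine already given | b |
| 5 | Pregnancy | c |
| 6 | Proven influenza (cut-off September 1, 2018) | d (cut-off September 1, 2019) |
| 7 | Non-allogeneic or syngeneic transplant | none |
| 8 | HIV | e |
| 9 | Cirrhosis | f |
| 10 | Latex hypersensitivity | none |
| 11 | Stem cell boost or donor lymphocyte infusion | g |
| 12 | Recent IVIG/SCIG | h |

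- Not carried over: 12 − 8 = 4 (items 1, 2, 7 and 10).
- Item 7 was settled at first enrolment: 4 − 1 = 3 that can newly arise.
- Item 1 is barred study-wide in C.11.b: 3 − 1 = 2 with no express exclusion for repeaters.

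**Step 2: ask whether the repeater list adds to C.4.b or replaces it.** If both lists applied, item 6 with its 2018 cut-off would still exclude a repeater for influenza in the previous season, and moving the date in item d would serve no purpose. The inclusion criteria point the same way. New subjects must be 3 to 23 months post-transplant, and the repeater inclusion list has no such window. Assuming about a year between enrolments, a subject who first entered at 12 months would be at about 12 + 12 = 24 months and would fail it. The repeater list therefore reads as stand-alone.

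**Step 3: ask whether earlier screening explains the omission.** HIV and cirrhosis were also cleared at first enrolment, yet both are listed again. That earlier clearance therefore does not account for leaving out the other standing conditions.

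**Step 4: see what remains for Guillain-Barre syndrome and latex.**

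| Provision | What it does | Why it is less than a listed exclusion |
|---|---|---|
| C.8.a item 2.a | Requires discontinuation when a medical condition makes participation contrary to the subject's interest | Mandatory, but turns on a judgment |
| C.8.a item 2.b | Lets a newly developed exclusion lead to discontinuation | Permissive |
| C.13.a and C.13.b | History, examination and eligibility review before each vaccination | For repeaters, the listed criteria omit both conditions |
| C.13, Events Which Warrant Withdrawal | Lets the investigator withdraw a subject for a clinically significant adverse event | Permissive; covers adverse events, not a history as such |
| Note closing the repeater exclusions | Allows vaccine 2 "unless it is deemed not medically safe to receive influenza vaccine" | A judgment, and only for the second dose |
| C.16.j item 6 | One case of acute limb or cranial-nerve weakness pauses the study for DSMB review | Study-level; does not address an individual's eligibility |

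No row states that a repeater with either condition is excluded.

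**The case against.** The best defence is that the repeater list is silent and overrides nothing. Repeaters keep their study ID and are not re-randomized, so they can be read as continuing subjects under C.8.a. Item 2.a there is mandatory once participation is judged to be against the subject's interest, and item 2.b speaks of any exclusion criterion, not only those on the repeater list. The withdrawal provision in C.13 gives allergic reaction to vaccine as an example only, so Guillain-Barre syndrome arising on study would plausibly qualify. A severe latex reaction at a study dose would plausibly be handled as a reaction to vaccine under C.13 and C.11.b.

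Most of this stands and narrows the gap. What remains is mainly Guillain-Barre syndrome unrelated to a study dose, and latex allergy first recognised away from one. For those cases the outcome still depends on judgment.

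A reader might infer more than the documents support in three ways:

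- That vaccine and egg allergy is an open gap as well. It is missing from the list, but C.11.b bars it for everyone.
- That the protocol admits a repeater with Guillain-Barre syndrome or latex allergy. It does not expressly exclude one; the provisions above still apply and may keep that person out.
- That re-listing HIV and cirrhosis shows an intention to let the other conditions through. It shows uneven drafting and nothing more.

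**Conclusion.** The inconsistency is real and minor. Two conditions that bar new subjects, Guillain-Barre syndrome and known latex hypersensitivity, are not expressly excluded for repeaters. Keeping such a person out rests on judgment-based or study-level safeguards.

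The conclusion assumes that the repeater list stands alone, as its re-dated influenza item indicates, and that either condition can appear or be recognised between seasons. The number of people affected cannot be derived from the documents. Few if any are likely: each repeater cleared C.4.b at first enrolment, and only the 2019-20 repeater season remains under version 6.0, dated August 12, 2019. Nothing here suggests that anyone was harmed, and no endpoint, sample size or analysis changes.

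**What to change.** Add C.4.b items 2 and 10 to the repeater exclusions. Restate item 1 there as well, so that the list agrees with C.11.b. Have sites ask repeaters about all three in the medical history review already scheduled at Visit 1 (C.14), and update the eligibility checklist to match. No new visit, test or analysis is needed.

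The cost is a short amendment, which under C.18.b goes to the FDA and the IRB and then has to reach four sites for the one remaining repeater season. A very small number of repeaters might be lost.
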